11.7 Confidentiality of study documents and patient records

The investigator must ensure anonymity of the patients; patients must not be identified by names in any documents submitted to Novartis. Signed informed consent forms and patient enrollment log must be kept strictly confidential to enable patient identification at the site.

11.8 Audits and inspections

Source data/documents must be available to inspections by Health Authorities.

11.9 Financial disclosures

Financial disclosures should be provided by study personnel who is directly involved in the treatment or evaluation of patients at the site - prior to study start.

12 Protocol adherence

Investigators ascertain they will apply due diligence to avoid protocol deviations. Under no circumstances should the investigator contact Novartis or its agents, if any, monitoring the study to request approval of a protocol deviation, as no authorized deviations are permitted. If the investigator feels a protocol deviation would improve the conduct of the study this must be considered a protocol amendment, and unless such an amendment is agreed upon and approved by the IRB/IEC/REB it cannot be implemented. All significant protocol deviations will be recorded and reported in the CSR.

Appendix 2: Study Schedules (Phase 1 and Phase 2)

Appendix 3: MPN-SAF

Appendix 4: Dynamic International Prognostic Scoring System (DIPSS)

Appendix 5: Subject Study Pill Diaries

Appendix 1 Co-medications which are known to prolong the QT interval and/or induce Torsades de Pointes, are strong CYP3A4/5 inhibitors and inducers, moderate CYP3A4 inducers, CYP2D6 substrates, or otherwise prohibited for use

Table of Contents

- A. Medication prohibited during the treatment period and 30 day follow-up for Study CLBH589x2106
- B. Medications which are known to prolong the QT interval and/or induce Torsades de pointes ventricular arrhythmia should be avoided
- C. Medications which are known strong CYP3A4/5 inhibitors to be used with caution
- D. Medications which are known CYP2D6 substrates to be used with caution
- E. Medications which are known to be moderate inducers of CYP3A4 are to be used with caution

A. Medication prohibited during the treatment period and 30 day follow-up for Study CLBH589x2106

The following medications are prohibited during this study:

1. Systemic steroids greater than 10 mg daily, unless use is part of a RUXOLITINIB dose tapering strategy ([Section 6.2.10](#))
2. Systemic anticoagulation, or drugs that inhibit platelet function, with the exception of:
 - Aspirin \leq 150 mg/day
 - Low molecular weight heparin (LMWH)
3. Any other investigational medication
4. Any other medication used for the treatment of myelofibrosis, including but not limited to the following:
 - Anagrelide
 - Busulfan
 - Hydroxyurea
 - Interferon
 - Lenalidomide
 - Thalidomide
5. Any medication which is known to be a strong CYP3A4 inducer* (e.g. avasimibe, carbamazepine, Phenobarbital, phenytoin, rifabutin, or St. John's wort)

*This list of strong CYP3A4 inducers was compiled from the FDA's "Guidance for Industry, Drug Interaction Studies;" from the Indiana University School of Medicine's "Clinically Relevant" Table; from the University of Washington's Drug Interaction Database; and from [Pursche et al \(2008\)](#).

6. Any use of hematopoietic growth factor receptor agonists (including but not limited to:erythropoietin, romiplostim, or eltrombopag). The use of G-CSF may be used after consultation with the sponsor. See [Section 6.3.2](#) for further details.

B. Medications which are known to prolong the QT interval and/or induce Torsades de pointes ventricular arrhythmia should be avoided

Patients, who are currently receiving treatment of the medications listed in [Table 2-1](#) and cannot either discontinue from this treatment or switch to an alternative medication prior to enrollment in a PANOBINOSTAT clinical study, will be excluded from the study. Patients enrolled in a PANOBINOSTAT clinical study may not begin treatment with any of the medications listed in [Table 2-1](#) unless discussed with the Sponsor and approval is granted by the Sponsor. The Sponsor may agree to temporarily discontinue PANOBINOSTAT treatment (e.g., for 72 hours) during administration with these drugs or withheld medications in [Table 2-1](#) for at least 72 hours when PANOBINOSTAT is to be administered.

NOTE: It is of great importance to avoid combining drugs listed below in [Table 2-1](#) and [Table 3-1](#) (CYP3A inhibitors) in combination with PANOBINOSTAT especially in the presence of electrolyte abnormalities, notably decreased potassium or magnesium levels commonly associated with diuretic usage.

In general, medications listed in [Table 2-1](#) should be avoided. Medications listed in [Table 3-1](#) and [Table 4-1](#) are to be used with caution when co-administered with PANOBINOSTAT. The use of any of the drugs in [Table 2-1](#), [Table 3-1](#), and [Table 4-1](#) in combination with PANOBINOSTAT must be discussed with the Sponsor.

Table 2-1 Medications which are known to prolong the QT interval and/or induce Torsades de pointes to be avoided

All Class IA antiarrhythmics 
• quinidine• procainamide• disopyramide• any other class IA antiarrhythmic drug
All Class III antiarrhythmics 
• amiodarone• sotalol• dofetilide• ibutilide• any other class III antiarrhythmic drug

Anti-infectives Macrolide antibiotics* 
• erythromycin• clarithromycin Quinolone antibiotics* 
• sparfloxacin Antifungals 
• pentamidine Antimalarials 
• halofantrine• chloroquine
Antihistamines 
• astemizole• terfenadine
Antinausea 
• chlorpromazine• domperidone• droperidol• dolasetron (intravenous and oral)[^]
Antipsychotics 
• thioridazine• mesoridazine• chlorpromazine• pimozide
Miscellaneous drugs 
• arsenic trioxide• bepridil• cisapride• levomethadyl• methadone

*Note: azithromycin, ciprofloxacin, levofloxacin, pefloxacin, ofloxacin, tosufloxacin, difloxacin, temafloxacin, fleroxacin, acrosoxacin, nalidixic acid and enoxacin are allowed.

[^]Intravenous dolasetron is contraindicated for preventing nausea and vomiting associated with chemotherapy based on FDA drug safety communication dated December 17, 2010. Based on this finding, both intravenous and oral dolasetron are prohibited to be taken with PANOBINOSTAT.

This is not a comprehensive list of medications which may prolong the QT interval and/or induce Torsades de pointes. This list of medications was developed in collaboration with an external cardiology consultant, and represents those medications which are deemed to have an unacceptable risk of co-administration with PANOBINOSTAT.

The following website may be referenced as a supplemental guide for drugs which have been associated with Torsades de pointes or prolonging the QT interval but at this point lack substantial evidence for causing Torsades de pointes:

<http://www.azcert.org/medical-pros/drug-lists/drug-lists.cfm> (Version 3/25/2008).

Medications listed on the website which do not appear in [Table 2-1](#) above may be used with caution at the discretion of the investigators.

Ondansetron (a known CYP2D6 substrate, see [Table 4-1](#)) has been associated with Torsades de points and QT prolongation but has not been shown to cause Torsades de pointes. Therefore, ondansetron is not per se prohibited to be combined with PANOBINOSTAT but caution is to be exercised and close monitoring for signs and symptoms of QT prolongation is recommended.

C. Medications which are known strong CYP3A4/5 inhibitors to be used with caution

The use of these drugs is prohibited during the first cycle of study treatment

PANOBINOSTAT is a substrate of CYP3A4 with minor involvement of CYP2D6, and CYP2C19 in *in vitro* evaluation of its metabolism. Thus, a clinical drug-drug interaction study was conducted using ketoconazole, a strong CYP3A inhibitor, in combination with PANOBINOSTAT in study [\[CLBH589B2110\]](#).

Multiple ketoconazole doses at 400 mg increased C_{max} and AUC of PANOBINOSTAT by 1.6- and 1.8-fold, respectively, but with no change in T_{max} or half-lives in 14 cancer patients. The less than 2-fold increase in PANOBINOSTAT AUC upon co-administration of a strong CYP3A inhibitor is considered a weak drug inhibition and not clinically relevant, as PANOBINOSTAT doses at least 2-fold greater than the evaluated 20 mg dose (i.e., 40 mg and 60 mg) have been safely administered in patients. Thus, co-administration of PANOBINOSTAT with a moderate or weak CYP3A inhibitor is allowed. However, clinical monitoring of signs and symptoms of PANOBINOSTAT treatment related adverse events is recommended when long-term (≥ 1 week) concomitant administration of any strong CYP3A inhibitors and PANOBINOSTAT is medically indicated or investigated in a clinical study.

RUXOLITINIB is metabolized in the liver predominantly by the CYP3A4 isozyme. With concomitant dosing of potent CYP3A4 inhibitors such as those medications listed in [Table 3-1](#), plasma exposure of RUXOLITINIB increases approximately 2-fold. Use of those medications listed in [Table 3-1](#) is strongly discouraged, and investigators should consider alternative therapies wherever possible. However, if the use of a potent CYP3A4 inhibitor is necessary for the sake of the patient's safety, then a dose reduction of ~50% of RUXOLITINIB is mandatory. See [Section 6.3.4](#) for further details of this dose reduction schema.

Based on the low overall bioavailability of topical ketoconazole, with very low systemic levels seen following topical administration, no dose adjustment of RUXOLITINIB is needed for use with topical ketoconazole. No dose adjustments are necessary when RUXOLITINIB is co-administered with erythromycin, or by extension, with other moderate or weak inhibitors of CYP3A4, including grapefruit juice.

Patients with impaired liver function (as defined by NCI CTEP criteria)¹ are recommended not to receive PANOBINOSTAT concomitantly with strong CYP3A inhibitors because potential interaction has not been established in this population.

Table 3-1 Medications which are known strong CYP3A4/5 inhibitors to be used with caution

Macrolide antibiotics*
• telithromycin
• troleandomycin
Antifungals (azoles)
• ketoconazole
• itraconazole
• posaconazole
• voriconazole
Antidepressants
• nefazodone
HIV protease inhibitors:
• indinavir
• nelfinavir
• ritonavir
• saquinavir
• lopinavir
Miscellaneous drugs or products
• ² Star fruit and pomegranate product and juice
• conivaptan

* azithromycin and regular orange juice are allowed.

Although clarithromycin is a known strong CYP3A inhibitor, it is also known to prolong QT intervals which is listed in [Table 2-1](#) and is prohibited to be taken with PANOBINOSTAT. This drug is thus not listed again in [Table 4-1](#).

This is not a comprehensive list of medications which may inhibit CYP3A4/5. The above list was compiled by using information listed under “draft guidance for industry, drug interaction studies, CDER 2006”, Indiana University School of Medicine drug interaction tables at <http://medicine.iupui.edu/clinpharm/DDIs/ClinicalTable.asp>, and “drug interaction database” from University of Washington. Additional updated versions with moderate and weak CYP3A inhibitors, which are meant to be used as a guide, may be found at the following website: <http://medicine.iupui.edu/clinpharm/DDIs/ClinicalTable.asp>.

D. Medications which are known CYP2D6 substrates to be used with caution

PANOBINOSTAT was also shown to be a CYP2D6 inhibitor (K_i 0.17 μM) *in vitro*. Thus, clinical drug-drug interaction study with PANOBINOSTAT as CYP2D6 inhibitor and dextromethorphan as CYP2D6 substrate was recently conducted in study [CLBH589B2109].

Multiple PANOBINOSTAT doses increased C_{max} and AUC of dextromethorphan by a mean of 1.8- and 1.6-fold respectively, but with no change in T_{max} in 17 cancer patients. An approximately 2-fold increase in dextromethorphan AUC upon co-administration with PANOBINOSTAT indicated that *in vivo* CYP2D6 inhibition of PANOBINOSTAT is weak.

As the study was conducted using a sensitive CYP2D6 substrate which resulted in a weak inhibition, drugs with a large therapeutic index such as anti-emetics, anti-hypertensives, and anti-depressants are generally safe to be co-administered with PANOBINOSTAT.

Patients should be carefully monitored for potential signs and symptoms of toxicity and may require dose titration or dose reduction of a sensitive CYP2D6 substrate which also have a narrow therapeutic window (e.g., the ratio of toxicity exposure ≤ 2 -fold higher than the efficacious or therapeutic exposure).

Table 4-1 Medications which are known CYP2D6 substrates to be used with caution

Beta blockers (listed below):	Antipsychotics (listed below):
S-metoprolol	aripiprazole
propafenone	haloperidol
timolol	risperidone
Antidepressants (listed below):	Antiarrhythmics (listed below):
amitriptyline	thioridazine
clomipramine	mexiletine
desipramine	flecainide
imipramine	Others (listed below):
fluoxetine	codeine
paroxetine	dextromethorphan
venlafaxine	tamoxifen
duloxetine	tramadol
Antiemetics (listed below):	
ondansetron [^]	

[^]Intravenous dolasetron is a CYP2D6 substrate and contraindicated for preventing nausea and vomiting associated with chemotherapy based on FDA drug safety communication dated December 17, 2010. Please see [Table 2-1](#).

This is not a comprehensive list of CYP2D6 substrates. Additional updated versions of this list, which are meant to be used as a guide, may be found at the following website: <http://medicine.iupui.edu/clinpharm/DDIs/ClinicalTable.asp>

E. Medications which are known to be moderate inducers of CYP3A4 are to be used with caution

During the study, the use of moderate CYP3A4 inducers (e.g. bosentan, efavirenz, etravirine, modafinil, nafcillin, ritonavir, talviraline, tipranavir) is discouraged, and investigators should seek alternatives where possible. No dose adjustment will be used when moderate CYP3A4 inducers are co-administered with RUXOLITINIB. However, any concomitant use of moderate CYP3A4 inducers must be documented.

This is not a comprehensive list of medications which may induce CYP3A4/5. The above list was compiled by using information listed under “draft guidance for industry, drug interaction studies, CDER 2006”, Indiana University School of Medicine drug interaction tables at <http://medicine.iupui.edu/clinpharm/DDIs/ClinicalTable.asp>, and “drug interaction database” from University of Washington.

References (available upon request)

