6.3.3 Prohibited concomitant therapy

The following medications are prohibited during the study:

- Any investigational medication (other than PANOBINOSTAT) that is not approved for any indication. Use of such medications within 30 days, prior to the first dose of study drug and during the study through the Safety Follow-up Visit is prohibited.
- Use of strong inducers of CYP3A4 (e.g. avasimibe, carbamazepine, phenobarbital, phenytoin, rifabutin, rifampin, St. John's wort) is not permitted at any time during the study. (See Appendix 1 for further details)
- Patients who are currently receiving treatment with any of the medications which have a relative risk of prolonging the QT interval or inducing Torsades de Pointes and cannot either discontinue this treatment or switch to a different medication prior to study enrollment, will be excluded from the study. Patients may not begin treatment with any of the medications while receiving study treatment unless approval is given by the Investigators to temporarily discontinue study treatment during administration with these drugs. Should a patient already enrolled on this study require short-term (i.e. approximately \leq 2 weeks) treatment with these drugs, study treatment must be interrupted for at least 72 hours prior to starting these drugs and should not resume until at least 72 hours after the last dose of such a drug or longer (i.e. 5 half-lives) as listed.
- Any use of drugs that interferes with coagulation or inhibits platelet function (including non-steroidal anti-inflammatory drugs), with the exception of:
 - Aspirin \leq 81 mg/day
 - LMWH, direct thrombin inhibitors, anti-10a inhibitors as long as INR remains less than 1.5
- Any other medication for the treatment of myelofibrosis, including but not limited to:
 - Hydroxyurea
 - Busulfan
 - Interferon
 - Lenalidomide

- Thalidomide
- Anagrelide
- Any hematopoietic growth factor receptor agonists (including but not limited to: erythropoietin, romiplostim, or eltrombopag). The use of G-CSF can be used as discussed in Section 6.3.2.

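### Appendix 1 part A item 2 does not match Section 6.3.3 on aspirin and anticoagulants, and nothing says which list prevails

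*Combined protocol and SAP*

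**What the plan says.** Section 6.3.3 opens with "The following medications are prohibited during the study". One entry covers "Any use of drugs that interferes with coagulation or inhibits platelet function (including non-steroidal anti-inflammatory drugs), with the exception of" two things: aspirin at 81 mg/day or less, and "LMWH, direct thrombin inhibitors, anti-10a inhibitors as long as INR remains less than 1.5". Exclusion criterion 9 uses the same aspirin figure for entry and excludes patients on therapeutic warfarin. Section 6.2.7 sends the reader to Section 6.3 for what is permitted and prohibited.

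Appendix 1 part A opens with "The following medications are prohibited during this study". Its item 2 covers "Systemic anticoagulation, or drugs that inhibit platelet function, with the exception of" aspirin at 150 mg/day or less, and LMWH. It has no INR condition and does not mention direct thrombin or anti-10a inhibitors. The part A heading reads "Medication prohibited during the treatment period and 30 day follow-up for Study CLBH589x2106"; the documents do not explain that study code, and it appears only in this appendix.

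The two lists are linked. Section 6.3.3 says that use of strong CYP3A4 inducers "is not permitted at any time during the study. (See Appendix 1 for further details", and the only matching entry in Appendix 1 is part A item 5, "Any medication which is known to be a strong CYP3A4 inducer". A reader who follows that reference arrives at the list that contains item 2.

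**The concern.** Both lists are current text and both claim to govern this study, yet they set different limits on drugs that affect bleeding. Section 1.4.2 names thrombocytopenia as the main overlapping dose-limiting toxicity. Under Section 6.2.5, a platelet count of 10,000/µl or more with a grade 3 bleed in Days 1-28 of the combination phase is a DLT, and a treatment-related hemorrhagic event of grade 3 or higher ends participation. Section 6.2.7 also ties the platelet threshold for holding drug to bleeding events.

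The affected drugs are foreseeable. Stable atrial fibrillation is compatible with entry, Section 1.1 describes a thrombotic tendency in this disease, and therapeutic warfarin is excluded, so the status of the alternatives matters. An investigator who opens only the appendix would find aspirin at 150 mg/day acceptable and a direct thrombin inhibitor not. One who opens only 6.3.3 would conclude the reverse on both, provided INR is below 1.5.

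**Working it through.** The plan states no figure that can be reproduced here. The check sets the two lists side by side.

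| Use | Section 6.3.3 | Appendix 1 part A item 2 |
|---|---|---|
| Aspirin up to 81 mg/day | excepted | excepted |
| Aspirin above 81, up to 150 mg/day | prohibited | excepted |
| Aspirin above 150 mg/day | prohibited | prohibited |
| LMWH, INR below 1.5 | excepted | excepted |
| LMWH, INR 1.5 or above | prohibited | excepted |
| Direct thrombin or anti-10a inhibitor, INR below 1.5 | excepted | prohibited (not among the exceptions) |
| Direct thrombin or anti-10a inhibitor, INR 1.5 or above | prohibited | prohibited |

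The LMWH rows take the INR condition in 6.3.3 to apply to all three classes in its phrase.

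**Size of the mismatch**

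- Aspirin ceiling: 150 − 81 = 69 mg/day.
- Anticoagulant classes excepted: three in 6.3.3 and one in the appendix, so 3 − 1 = 2 classes differ.
- Citations of Appendix 1 within Section 6.3: three in 6.3.2 (strong CYP3A4 inhibitors, moderate CYP3A4 inducers, CYP2D6 substrates), one in 6.3.3 (strong CYP3A4 inducers) and one in 6.3.4 (strong CYP3A4 inhibitors). That is 3 + 1 + 1 = 5, of which none concerns aspirin or anticoagulants and one leads to part A.

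**What each reading gives**

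- Lists cumulative (a drug must pass both): aspirin to 81 mg/day, and LMWH only, with INR below 1.5. Direct thrombin and anti-10a inhibitors are barred.
- Section 6.3.3 governs: aspirin to 81 mg/day, and all three anticoagulant classes while INR is below 1.5.

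The two readings agree on aspirin and on the INR condition for LMWH. They differ only on direct thrombin and anti-10a inhibitors with INR below 1.5. The 150 mg/day figure holds only if the appendix overrides 6.3.3, and nothing in the documents supports that.

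**Does any analysis depend on it?** Section 10.1.3 defines no per-protocol set. Evaluability for the dose-determining set (Sections 6.2.3 and 10.1.4) rests on DLT status, observation time, completed tests and study-drug intake, not on concomitant medication. Section 10.3 lists and summarizes deviations. No estimate or decision rule uses the aspirin or anticoagulant limits.

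**The case against.** The strongest reply is that the protocol already shows which rule is meant. Exclusion criterion 9 gives 81 mg/d, Section 6.2.7 directs readers to Section 6.3, Section 6.3.2 adds instructions for starting LMWH, and the appendix heading carries an unexplained study code. The lists can also both be obeyed by reading them cumulatively. For the two anticoagulant classes the appendix is the stricter text, and the patient diaries require physician approval of all medications. Much of this stands: it makes 6.3.3 the likely intent and keeps the practical risk small. It does not remove the mismatch. Part A says it applies to this study, 6.3.3 itself leads readers there, and the cumulative reading would leave the 6.3.3 exception for two classes without effect.

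Three stronger readings are tempting, and the documents do not support them.

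- A reader might infer that the protocol gives flatly opposite orders on the two classes, so that deviation status cannot be determined. Both texts are prohibitions with exceptions, and an exception in one does not cancel a prohibition in the other. Each reading gives a definite answer; what is missing is a statement of which reading applies. The same reading must be used for aspirin and for anticoagulants.
- A reader might infer that the appendix relaxes the rule on NSAIDs because it does not name them. Item 2 already bars drugs that inhibit platelet function, which is where 6.3.3 places NSAIDs.
- A reader might infer an effect on DLT rates or trial results. None can be derived from the documents.

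**Conclusion.** The point holds as an inconsistency between two current lists that bears on safety. The 150 mg/day ceiling conflicts with 6.3.3 and exclusion criterion 9, a difference of 69 mg/day. Direct thrombin and anti-10a inhibitors, excepted in 6.3.3 while INR is below 1.5, are missing from the appendix exceptions, and so is the INR condition on LMWH. The only use whose status turns on the choice between the two plausible readings is that of those two classes with INR below 1.5.

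The conclusion assumes that part A is meant to apply to this trial, as its opening line says. Only patients taking aspirin above 81 mg/day, LMWH with INR at or above 1.5, or one of the two classes could be affected. Their number is not given and may be zero. No sample size, power, analysis set or efficacy result changes. The correction should be made because a stated safety limit is wrong in one place and costs almost nothing to put right.

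**What to change.** Replace the text of Appendix 1 part A item 2, including its exceptions, with one line that refers the reader to Section 6.3.3 for all anticoagulant and antiplatelet drugs. The limits then stand once. If the investigators do intend to bar direct thrombin and anti-10a inhibitors, they should amend 6.3.3 rather than leave the change in the appendix.

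In the same amendment, correct the study code in the part A heading and in the appendix's contents list, and check the remaining part A items against Section 6.3. Item 6, for example, requires consultation with the sponsor before G-CSF, where 6.3.2 leaves it to the investigator's discretion while study drug is withheld. The cost is a wording change to one appendix; Section 6.3.3 changes only if the investigators choose the stricter rule.
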